4.3.5. Rationale for Standard of Care Comparator

In this study, BCV will be compared with local institutional standard of care (SoC). A standard placebo-controlled design is not considered to be an ethical or practical option because AdV infection or disease can be rapidly fatal in this population. Similarly, an active control study design, in which patients would be randomized to BCV or IV CDV, is problematic because CDV

is not approved for this indication, is not standardly administered to all patients with AdV infection, and is not licensed for any indication in some countries. Furthermore, when IV CDV is used to treat AdV in HCT recipients, the dose, regimen and duration of treatment are not standardized, with regimens varying between 5 mg/kg QW to 1 mg/kg three times weekly, which may be modified according to patient response. The use of pre- and post- dose IV hydration and the use of probenecid are also variably applied. Finally, a significant percentage of patients with AdV infection have renal insufficiency, which is a noted contraindication for IV CDV (Mori 2003, Vistide Package Insert [Gilead Sciences 2010]). Therefore, physician-selected SoC represents the optimal comparator for this study, providing an opportunity to observe the efficacy and safety/tolerability of oral BCV vs. usual care for this condition, for which there are no approved therapies.

4.3.6. Rationale for Open Label Design

Blinding a study in which subjects are randomized to either oral BCV or a SoC arm that could include IV CDV is prohibitively difficult. Co-administration of probenecid is recommended to reduce renal toxicity (Vistide Package Insert [Gilead Sciences 2010]). Probenecid would, therefore, need to be provided under double-blind, double-dummy conditions. However, at the doses required, probenecid is associated with side effects, such as nausea, which would functionally unblind the treatment assignment. Administration of IV CDV also typically requires pre- and post-dose IV hydration which would have to be administered to all subjects to maintain the blind. This IV fluid load is associated with its own risks, particularly for small children, which raises ethical concerns for subjects randomized to oral BCV.

For these reasons, this study will be conducted as an open-label investigation. SoC will be according to local guidelines and institutional practice and may include administration of IV CDV, reduction in immunosuppression or other approaches not prohibited by this protocol. Given that the primary endpoint of the study is objective (clearance of AdV DNA from the plasma), biased assessment of the primary endpoint is unlikely.

[figure not shown]
4.3.7. Rationale for Primary Efficacy Endpoint and Secondary Endpoints

Powering a study for superiority on the basis of mortality was not considered ethical or feasible due to the large number of subjects that would need to be included. Multiple non-mortality clinical outcomes were considered as potential primary endpoints (such as progression of AdV disease or infection) and were rejected for a variety of reasons, including: (1) lack of consensus definitions of AdV disease and progression; (2) multiple etiologies that can result in similar signs/symptoms, and (3) the reluctance to require invasive diagnostic procedures to document progressive AdV disease (e.g., liver biopsy to document AdV hepatitis). For example, respiratory compromise can be the result of worsening AdV disease, the sequelae of the patient's conditioning regimen, or another infectious etiology; and renal dysfunction can be the culmination of multiple nephrotoxic insults, including AdV disease, and is commonly observed after CDV administration as well other known nephrotoxic medications. Gut injury is perhaps even more complicated with clinical, gross pathology and even histopathologic analysis unable to differentiate from progression of AdV disease, gut GVHD, and injury related to prolonged oral administration of BCV. In contrast, a primary endpoint based on control of AdV viremia is considered to be both feasible and clinically relevant.

The primary efficacy endpoint selected for this study is the time-averaged area under the concentration-time curve (AAUC) for plasma AdV viremia (\log_{10} copies/mL) through Week 16 post-randomization. This viral AAUC endpoint was selected based on evidence collected from prior BCV clinical trials and expanded access programs, as well as data from the literature evaluating SoC, showing that virologic response is predictive of clinical outcomes. AdV viremia has been demonstrated in natural history studies to be a valid predictor of disease-related outcomes, with thresholds of peak viremia identified which predict significant changes in expected survival, thus supporting the use of AdV viremia as a surrogate that is reasonably likely to predict clinical benefit. In addition, the positive impact on survival has been noted with reductions in AdV viral load following investigational interventions, including with adoptive T cells (Feucht 2015), IV CDV, and BCV (see Section 4.3.7.1 and Section 4.3.7.2).

To illustrate the clinical relevance of this endpoint, Chimerix has analyzed the data from pediatric HCT subjects enrolled in Cohorts A and B in the CMX001-304 study with AdV viral load ≥ 1000 copies/mL at baseline who were within 100 days of transplant ($n = 40$). In this group, 28% (11 of 40) subjects died by Week 16. A boxplot looking at distribution of AAUC through Week 16 by vital status (i.e., alive or dead) at Week 16 shows that survivors had reduced AAUC when compared with non-survivors (t-test $p = 0.11$) (Figure 2).

Figure 2: Study CMX001-304: AAUC through Week 16, Mortality at Week 16

Similar analyses have been conducted for two retrospective patient cohorts: a historical dataset dating back more than 10 years from Royal Manchester Children’s Hospital in the United Kingdom (UK) (the “Manchester Cohort”) (Figure 3) and preliminary data from three countries (France, Spain, and UK) from the AdVance study (Figure 4), which is a natural history study sponsored by Chimerix that will explore the association of AdV viremia, response to SoC therapy, and clinical outcomes (including overall survival and non-relapse mortality) in a contemporary multicenter cohort. The results from these two retrospective patient cohorts also support the correlation between the proposed endpoint (viral AAUC) and mortality under SoC

treatment with IV CDV (Manchester Cohort n = 24, p = 0.0032; AdVance n = 51, p = 0.007). (Note that a Manchester Cohort analysis looking at AAUC vs. mortality was not available in time to contribute; therefore, a previous analysis looking at time-averaged area under the curve minus baseline, or AAUCMB, is presented.)

Figure 3: Manchester Cohort: AAUCMB through Week 16, Mortality at Week 16

[figure not shown]
[figure not shown]

Figure 4: AdVance Study: AAUC through Week 16, Mortality at Week 16 (Preliminary Data from UK, Spain, and France)

A viral AAUC endpoint also provides the opportunity to correlate total viral burden with secondary endpoints of clinical outcomes, including all-cause and non-relapse mortality, as well as other clinical benefits, such as decreased progression to Adv pneumonia, and decreased number of days spent in the hospital or intensive care unit (ICU).

The study will also provide a holistic assessment of safety that includes the known side effects of oral BCV (GI toxicity) and IV CDV (renal injury). Immunosuppressant therapies utilized in the study will be recorded to document that short course BCV therapy and updated safety management guidance has mitigated the overuse of steroids observed in the CMX001-301 study (Section 4.2.3.1). Though it is anticipated that control of AdV replication will limit resulting organ damage and numerically improve survival in patients treated with oral BCV, a non-inferiority analysis of overall mortality at Week 16 between the BCV and SoC arms is included as a key secondary efficacy endpoint in order to rule out an untoward effect of BCV on outcomes.

4.3.7.1. Study CMX001-304

In a landmark analysis of data from Study CMX001-304, lower mortality outcomes were observed among subjects with early virologic response across both Cohort A (localized or asymptomatic AdV infection) and Cohort B (disseminated disease). Specifically, improved survival was observed among pediatric subjects with an undetectable viremia result at Week 4 (mortality 24% Cohort A and 29% Cohort B vs. 44% and 47%, respectively among non-responders who did not achieve undetectable AdV viremia at Week 4) (see Table 4). Pediatric subjects with disseminated disease (Cohort B) who achieved undetectable AdV viremia by Week 6 also had an improved overall survival (25% mortality vs. 54% mortality in pediatric subjects who did not achieve undetectable AdV viremia at Week 6). Similar observations were made in adult subjects, although overall survival rates were lower.

Table 4: Study CMX001-304: Early Virologic Response and Mortality Outcome

Responder Definition	Pediatrics			Adults		
	Proportion Responder ^a	Mortality among Responders	Mortality among Non-responders	Proportion Responder ^a	Mortality among Responders	Mortality among Non-responders
Cohort A (localized or asymptomatic AdV infection)						
Undetectable at Week 4	17/26 (65%)	4/17 (24%)	4/9 (44%)	7/13 (54%)	3/7 (43%)	5/6 (83%)
Undetectable at Week 6	17/25 (68%)	5/17 (29%)	2/8 (25%)	8/13 (62%)	4/8 (50%)	4/5 (80%)
Cohort B (disseminated AdV disease)						
Undetectable at Week 4	24/43 (56%)	7/24 (29%)	9/19 (47%)	9/26 (35%)	5/9 (56%) ^b	15/17 (88%)
Undetectable at Week 6	28/41 (68%)	7/28 (25%) ^b	7/13 (54%)	10/24 (42%)	5/10 (50%) ^b	13/14 (93%)

^a Denominator reflects subjects with baseline AdV viremia still on study at Week 4 or Week 6.

^b $p < 0.05$ vs. non-responders, Cox model for time to death.

Note: Cohort A total n (pediatric n, adult n): Enrolled 65 (42, 23), Week 4: 39 (26, 13), Week 6: 38 (25, 13).

Note: Cohort B total n (pediatric n, adult n): Enrolled 93 (58, 35), Week 4: 69 (43, 26), Week 6: 65 (41, 24).

[figure not shown]

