- To assess immunologic predictors of virologic response (all subjects) and relapse (among subjects with confirmed AdV clearance from plasma)
- To evaluate exploratory biomarkers for BCV-related gastrointestinal (GI) toxicity (e.g., citrulline, suppression of tumorigenicity-2 [ST2], T cell immunoglobulin mucin-3 [TIM3], and C-reactive protein [CRP])
- To assess healthcare resource utilization

Methodology: This is a randomized, open-label, multi-center study of the safety, overall tolerability, and antiviral activity of BCV, as compared with SoC, in pediatric recipients of high-risk (i.e., T cell-depleted) allogeneic HCT. Pediatric patients with AdV detected in plasma within the previous 21 days and for the first time since their qualifying transplant may be screened for participation in the study. Subjects who meet all applicable entry criteria will be randomized in a 2:1 ratio to receive either BCV or SoC. The day of randomization is defined as Day 1. During randomization, subjects will be stratified based on the following variables: last (non-baseline) screening AdV viremia ($\geq 10,000$ copies/mL vs. $< 10,000$ copies/mL), time from transplant to randomization (≥ 28 days vs. < 28 days), and T cell-depletion methodology (receipt of alemtuzumab or ex vivo depletion vs. receipt of anti-thymocyte globulin [ATG]). Subjects randomized to receive BCV will be treated until AdV deoxyribonucleic acid (DNA) is confirmed to be undetectable in plasma, up to a maximum of 16 weeks post-randomization. Subjects randomized to the SoC arm will be managed according to local or institutional practice guidelines for the treatment of AdV infection. All subjects, regardless of treatment assignment, will be followed in the study for a total of 36 weeks post-randomization. Subjects will be assessed on a weekly basis through Week 16, with additional assessments performed at Weeks 24 and 36 post-randomization. The data collected through Week 16 will comprise the primary data set for the study; hence, the primary database will be locked and analyzed following capture of data for all subjects through Week 16. In addition, all subjects (both BCV and SoC recipients) will be encouraged to enroll in the BCV Registry (Study CMX001-333) to assess the longer-term impact of exposure to BCV.

Number of Subjects (Planned):

The study will target the enrollment of a total of approximately 141 subjects, with 94 subjects randomized to the BCV arm and 47 subjects randomized to the SoC arm.

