4. INTRODUCTION

4.1. Background

In immunocompetent individuals, adenovirus (AdV) infections and resulting illnesses are generally mild, typically self-limited and resolve without sequelae (Ison 2002a, Ison 2006, Lenaerts 2008). However, patients who have undergone allogeneic hematopoietic cell transplant (HCT) are at especially high risk for developing AdV disease and, in this susceptible population, the development of AdV infection associated with viremia is much more prevalent and rapidly fatal without treatment (Florescu 2012, Ison 2006, Lion 2014, Sandkovsky 2014). Children are at higher risk of infection and manifestations can be severe among pediatric patients (Lion 2014). Common disease manifestations of AdV infection in immunocompromised patients are serious and include hemorrhagic cystitis, pneumonia and bronchiolitis obliterans, liver failure, severe gastrointestinal (GI) disease (Ison 2006, Legrand 2001) and renal damage, such as nephritis and obstructive nephropathy (Mori 2003).

The incidence of AdV infection and risk of serious disease is generally higher among children (Chakrabarti 2000, Howard 1999, Ison 2002b, Mynarek 2014) as well as recipients of T cell-depleted grafts (Chakrabarti 2002, Lee 2011, Mynarek 2014) and patients with acute graft versus host disease (GVHD) (Flomenberg 1994, Lion 2014, Runde 2001); risk is also high among recipients of unrelated or human leukocyte antigen-mismatched transplants due to profound and persistent immunodeficiency (Baldwin 2000, Bruno 2003, Howard 1999, Lion 2014). Earlier detection of AdV viremia after HCT and higher viral loads have also been correlated with increased risk of fatal outcome (Mynarek 2014). Severe and persistent lymphopenia is also associated with increased incidence of AdV infection, as well as progression to disseminated and often fatal AdV disease (Chakrabarti 2002, 2007, Lion 2014). The mortality rate for patients undergoing HCT approaches 26% for all symptomatic patients, and can reach 50% to 80% in pediatric patients with disseminated AdV disease (Lion 2014).

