6.3. Number of Subjects

Approximately 141 pediatric subjects will be randomized between the two treatment arms in a 2:1 ratio to receive either BCV or SoC.

Table 5: Schedule of Study Assessments/Procedures

Assessment/Procedure	Screening ^a	Baseline ^b	Treatment Period ^c																Follow-up ^e	
			1	2	3	4	5*	6	7*	8	9*	10*	11*	12	13*	14*	15*	16	24*	36*
Study Week	-3 to -1	0	1	2	3	4	5*	6	7*	8	9*	10*	11*	12	13*	14*	15*	16	24*	36*
Planned Study Day	-21 to -1	1	8	15	22	29	36	43	50	57	64	71	78	85	92	99	106	113	169	253
Written informed consent ^d	X																			
Assess/review entry criteria	X	X																		
Assess/review medical history	X	X																		
Physical examination ^e	X	X				X				X				X					X	
HCT comorbidity ^f		X																		
PELOD score ^g		X	←----- X -----→																	
Urine pregnancy test ^h	X	X				X				X				X					X	
HIV, HBV, HCV tests ⁱ	X																			
Randomization		X																		
BCV ^j			←----- X -----→																	
SoC ^k			←----- X -----→																	
Height/length		X																		
Body weight ^l	X	X		X																
Plasma for real-time AdV and CMV ^m and storage for other virologic assessments ⁿ	X	X	X	X	X	X	X	X	X	X	X	X	X	X	X	X	X	X	X	X
Urine, stool and respiratory secretion sample for AdV assessment ^o		X				X		X		X				X					X	
Stool collection for storage (possible future virologic analyses) ^p		X	X	X	X	X	X	X	X	X	X	X	X	X	X	X	X	X		
Assess clinical signs and symptoms for AdV disease	X	X	X	X	X	X	X	X	X	X	X	X	X	X	X	X	X	X	X	X

Assessment/Procedure	Screening ^a	Baseline ^b	Treatment Period ^c																Follow-up ^e	
			1	2	3	4	5*	6	7*	8	9*	10*	11*	12	13*	14*	15*	16	24*	36*
Study Week	-3 to -1	0	1	2	3	4	5*	6	7*	8	9*	10*	11*	12	13*	14*	15*	16	24*	36*
Planned Study Day	-21 to -1	1	8	15	22	29	36	43	50	57	64	71	78	85	92	99	106	113	169	253
Clinical chemistry and hematology	X	X	X	X	X	X	X	X	X	X	X	X	X	X	X	X	X	X	X	X
Coagulation panel	X	X	X	X	X	X	X	X	X	X	X	X	X	X	X	X	X	X	X	X
Lymphocyte (CD4+/CD8+) subsets and other potential immunologic predictors of virologic response		X	X	X	X	X	X	X	X	X	X	X	X	X	X	X	X	X	X	X
Urinalysis	X	X				X				X				X				X		
Diarrhea symptoms assessment and review subject e-diary	X	X	X	X	X	X	X	X	X	X	X	X	X	X	X	X	X	X	X	
Perform drug accountability		X	X	X	X	X	X	X	X	X	X	X	X	X	X	X	X	X	X	
Clinical AE assessment ^d		X	X	X	X	X	X	X	X	X	X	X	X	X	X	X	X	X	X	X
Review and record all concurrent medications	X	X	X	X	X	X	X	X	X	X	X	X	X	X	X	X	X	X		

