10.2. Assessment of Clinical Efficacy

Subjects will be monitored for clinical signs and symptoms of AdV disease at every visit throughout the study. Investigators will be prompted to enter symptom information into the eCRF at each visit. Definitions and criteria for assessing probable and definitive AdV disease are summarized below and in [Appendix 5](#).

AdV Infection:

- AdV infection defined as positive AdV test, regardless of the biological specimen analyzed
- Systemic AdV infection or viremia is defined as positive AdV PCR, virus isolation, or antigen detection in peripheral blood

AdV Disease:

- Probable AdV disease is defined as AdV infection plus symptoms and signs attributed to AdV without histological confirmation
- Definitive AdV disease is defined as AdV infection plus symptoms and signs attributed to AdV with histological confirmation

Disseminated AdV Disease defined as:

- AdV disease (probable or definitive) in one or more organ systems with AdV viremia
- AdV disease (probable or definitive) in two or more organ systems without AdV viremia

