12.1. Determination of Sample Size

A total of approximately 141 subjects will be enrolled into this study. Sample size calculations were based on the primary endpoint, i.e., AAUC through Week 16. Assuming the observed standard deviation of 1.03 log₁₀ copies/mL in AAUC at Week 16 from a comparable subset of SoC subjects, the study has > 90% power with the currently planned sample size to demonstrate superiority of BCV vs. SoC, given that the true difference in means is > 0.6 log₁₀ copies/mL (i.e., an effect size of ~ 0.58). In addition, the overall mortality at Week 16 non-inferiority comparison will have > 80% power in the event that the expected mortality for SoC is 20% to 30% and there is a true mortality advantage of 6% to 9% in favor of BCV ([Feghoul 2015](#), [Hiwarkar 2017](#), [Mynarek 2014](#)).

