- Multiple imputation, where the missing part of the trajectory is imputed based on a model ([Rubin 1978](#)). This imputation is repeated to create multiple simulated data sets (e.g., 5-times the number of deaths plus drop-outs). Each of these simulated data sets is analyzed independently and the results from these analyses are pooled to yield a final inference.
- Undetectable imputation, where the missing part of the trajectory is imputed as undetectable.

In addition to the above, three other supportive analyses are proposed to directly account for subjects who die prior to Week 16:

- Baseline imputation, where the missing part of the trajectory for deaths only is imputed at the baseline value for the subject.
- Analysis of time below the detection limit, whereby subjects who die are considered to be above the detection limit after death. This approach will be repeated using time below 1000 copies/mL, which is a clinically-meaningful level of viremia often signaling viral control vs. need to address in clinical practice.
- Generalized pairwise comparisons of prioritized outcomes ([Buyse 2010](#)). In this approach, all BCV subjects are compared with all SoC subjects in the same stratum. Comparisons will be made based on the following hierarchy:
 - Alive or dead at Week 16
 - If both die before Week 16, compare time to death
 - If both are alive at Week 16, compare AAUC

Each comparison yields a favorable, unfavorable, or neutral result. The “proportion in favor of treatment” (Δ) is the net difference between the number of favorable pairs and the number of unfavorable pairs divided by the total number of pairs. The null hypothesis $H_0: \Delta=0$ is tested using a randomization test.

Another important factor that may influence the primary inference is the imputation of undetectable and BLQ AdV viremia values, with additional sensitivity analyses conducted in order to assess the potential impact of this imputation:

- Impute all undetectable/BLQ values at 1 copy/mL (i.e., 0 log₁₀ c/mL)
- Impute all undetectable/BLQ values at 189 copies/mL
- Impute all values < 1000 copies/mL at 1 copy/mL

In addition, a supportive analysis of overall mortality (adjusting for advanced baseline disease, [Matthes-Martin 2008](#)) will examine the non-inferiority of BCV treatment to SoC. No negative impact on mortality will be concluded if the upper bound of the one-sided 95% confidence

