12.9. Subgroup Analyses

The primary and all-cause mortality endpoints will be analyzed by various subgroups, including, but not limited to, each of the stratification factors, sex, age, race, transplant characteristics, underlying disease (malignant, non-malignant), advanced disease status, and investigator's intended SoC selected at the time of randomization. Multivariate modelling will be considered and defined in the SAP.

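### The Week 16 mortality non-inferiority analysis does not use AdV disease at Day 1, a baseline status the trial needs anyway; adjusting for it is a cheap gain in precision of uncertain size

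*Combined protocol and SAP*

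**What the plan says.** Section 12.4.1 plans a "supportive analysis of overall mortality (adjusting for advanced baseline disease"), with non-inferiority concluded if the upper limit of a one-sided 95% interval for the BCV minus SoC difference is below 10 percentage points. No other covariate is named for this analysis, and the method of adjusting an absolute difference is not given. Section 12.4.2 plans Cochran-Mantel-Haenszel tests over the stratification factors for dichotomous secondary endpoints, but those yield odds ratios, and AdV disease is not a stratification factor (Section 8.8).

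The term advanced baseline disease is not defined. Two things suggest that it means the disease for which the child was transplanted: the source cited for it is, by its title, about risk-adjusted outcome in pediatric transplantation, and Section 12.9 lists "underlying disease (malignant, non-malignant), advanced disease status" side by side.

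AdV disease at Day 1 appears elsewhere. Section 4.3.7.1 sets out mortality by early virologic response "across both Cohort A (localized or asymptomatic AdV infection) and Cohort B (disseminated disease"). Signs and symptoms of AdV disease are assessed at baseline (Table 5), and footnote b asks for baseline procedures before randomization. Section 5.3.2 has a progression endpoint among children asymptomatic at baseline and a resolution endpoint among those with probable or definitive disease at baseline. Section 10.2 counts as disseminated any "AdV disease (probable or definitive) in one or more organ systems with AdV viremia"; since every child must be viremic to enter, probable or definitive disease at Day 1 falls under that label.

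**The concern.** The mortality comparison is the key secondary endpoint. Section 4.3.7 says that it is there to rule out an untoward effect of BCV on outcomes. It rests on 47 SoC subjects and, as shown below, has little power to spare. A baseline variable that may predict death, and that has to be classified for other endpoints, is left out of its model.

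What is at stake is the width of the interval and how easily the result can be read if the arms happen to differ in the share of children with AdV disease. The validity of the test is not at stake.

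**Working it through.** **Inputs from the documents.** Arm sizes: "with 94 subjects randomized to the BCV arm and 47 subjects randomized to the SoC arm". Margin 10 points, one-sided 5%. SoC mortality 20% to 30%, with BCV 6 to 9 points lower (Section 12.1), read as the pairs 20/14 and 30/21. Pediatric deaths in Table 4 at the Week 4 landmark: Cohort A (4+4)/26, Cohort B (7+9)/43.

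**Inputs that are assumed.** The share π of children with AdV disease at Day 1, and mortality m1 with and m0 without disease, are not given for this trial. I use π = 20% to 40% and two mortality gaps, besides the Table 4 gap.

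**The plan's own figure.** Stated non-inferiority power is above 80%. With the unpooled normal formula, power = Φ[(0.10 + d)/SE − 1.645]:

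- 20/14: SE = √(0.20×0.80/47 + 0.14×0.86/94) = 0.0684; Φ(0.160/0.0684 − 1.645) = 75.6%.
- 30/21: SE = √(0.30×0.70/47 + 0.21×0.79/94) = 0.0790; Φ(0.190/0.0790 − 1.645) = 77.7%.

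A Newcombe (Wilson score) bound gives 81.1% and 81.8%. So the stated figure is reached with a score-type interval and missed by 2 to 4 points with the unpooled one.

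**Precision from adjustment.** With overall mortality P = π·m1 + (1−π)·m0, the covariate explains R² = π(1−π)(m1−m0)²/[P(1−P)], and the standard error is multiplied by √(1−R²).

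| Gap | π | P | R² | SE smaller by |
|---|---|---|---|---|
| Table 4, Week 4: 37.2% vs 30.8% | 43/69 = 62% | 34.8% | 0.4% | 0.2% |
| Assumed 40% vs 15% | 20% | 20.0% | 6.3% | 3% |
| Assumed 40% vs 15% | 40% | 25.0% | 8.0% | 4% |
| Assumed 50% vs 12% | 20% | 19.6% | 14.7% | 8% |
| Assumed 50% vs 12% | 40% | 27.2% | 17.5% | 9% |

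With R² = 0.4%, unpooled power goes from 75.6% to 75.7% (20/14) and from 77.7% to 77.8% (30/21). With R² = 15%, it goes to 81.3% and 83.3%. To reach 80% with the unpooled formula, R² would have to be about 11.6% and 6.3%.

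**Chance imbalance.** Its standard deviation is √[π(1−π)(1/94 + 1/47)], which is 7.1 points at π = 20% and 8.8 points at π = 40%. One standard deviation moves the crude mortality difference by 0.38 × 7.1 = 2.7 to 0.38 × 8.8 = 3.3 points under the assumed 50% vs 12% gap. Under the Table 4 gap (π = 62%) it is 0.064 × 8.7 = 0.6 points.

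**How firm is the Table 4 gap?** The difference is 6.4 points, with a 95% interval of about −16 to +29 (Fisher p = 0.61). The Week 6 landmark gives 7/25 (28%) against 14/41 (34%).

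**The case against.** The strongest objection is that the documents do not show AdV disease at Day 1 to be a strong predictor of death in this population.

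- The sponsor's pediatric figures differ by only 6 points.
- Section 4.1 says that mortality "can reach 50% to 80% in pediatric patients with disseminated AdV disease", but that is an upper-type figure, and the same sentence puts all symptomatic patients at about 26%.
- Section 7.2 excludes many of the sickest children: ventilation, recent oxygen, vasopressors, creatinine clearance below 30 mL/min, and aminotransferases above five times the upper limit, which by itself removes most hepatic AdV disease as Appendix 5 defines it.
- Cohort A included localized infection, so the earlier split is not the same as none vs probable/definitive.

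All of this stands, and it is why no large gain can be promised. It does not show that the gain is nil. The landmark data leave out deaths before Week 4, every child received BCV, and the interval reaches +29 points.

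A second objection is that Table 5 schedules signs and symptoms, while Appendix 5 also asks for imaging, endoscopy, biopsy or exclusion of other causes. Classification will therefore depend on local work-up. That stands in part: misclassification would shrink the gain. But the status has to be assigned anyway for the progression and resolution endpoints, so the covariate needs no new data.

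A third is that Section 12.9 has an open subgroup list and leaves multivariate modelling to the SAP. That answers any complaint about subgroups. It does not settle the covariates of the non-inferiority analysis, which is better fixed before outcomes accumulate in an open-label trial.

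**Conclusion.** The omission is real and worth correcting, as a free improvement of uncertain size. The standard error would fall by between almost nothing (Table 4 gap) and 8% to 9% (50% vs 12% mortality, 20% to 40% prevalence). The upper figure rests on assumptions: prevalence and the 12% are in no document, and 50% is only the low end of a literature range that may not apply to the children enrolled.

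A reader might infer more, and the documents do not support it:

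- *That imbalance could move the result by a third of the margin.* The 3.3 points above need the assumed 50% vs 12% gap; the sponsor's own gap gives 0.6. Nor is chance imbalance a bias, because the interval already allows for it.
- *That the AAUC model needs the same term.* Continuous baseline viremia is already in the ANCOVA. The sample size rests on a single spread ("Assuming the observed standard deviation of 1.03 log₁₀ copies/mL in AAUC at Week 16"), and no figure says how much of it AdV disease would explain beyond viremia.
- *That the subgroup list is defective.* It is expressly not exhaustive.

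**What to change.** In the SAP, for the Week 16 mortality non-inferiority analysis:

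1. Add AdV disease at Day 1 (none vs probable/definitive by Appendix 5, judged on information up to randomization) as a covariate alongside the one already planned. Say how children with symptoms that do not meet the probable criteria are coded.
2. Obtain the absolute risk difference by standardising the model's predicted risks over the covariates, so that it stays on the scale of the 10-point margin, and name the interval method.
3. Define advanced baseline disease.

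Naming AdV disease at Day 1 in Section 12.9 is optional. The AAUC model can stay as it is.

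The cost is SAP wording and one degree of freedom, against roughly 23 to 34 expected deaths (16% to 24% of 141). Sample size, visits and data collection do not change. If the covariate turns out to be weak, little is lost.
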